### **Lower Limb Candidate Predictors**

As there is currently no agreed method of classifying lower limb surgeries systematically as it pertains to postoperative pain, we reviewed the literature and consulted an orthopedic surgeon specializing in foot and ankle surgery ([name]) to categorize surgeries into a ranked list by anatomy, clinical similarity (e.g. fusion), and known risk factors of increased postoperative acute pain or rebound pain. If multiple surgeries are present, the surgery in the category that is deemed the most involved (i.e. higher ranking) will be selected as the primary surgery.

The following a-priori predictors were included:

- Patient will be assigned one main surgical type (i.e. surgery type is considered one class/categorical variable with Group 9 Soft tissue only as the reference):
  - 1= Fusion/Osteotomy of Ankle/Hindfoot/Midfoot (10,18,19)
  - 2= Total Ankle Replacement (18)
  - 3= Acute Bony Trauma (18–22)
  - 4= Hallux Valgus Surgeries (18)
  - 5= Hardware Removal (18)
  - 6= Amputations
  - 7= Other Ankle/Hindfoot/Midfoot bony procedure (19,23,24)
  - 8= Other Forefoot bony procedure (19,23,24)
  - 9= Soft tissue only (8,18)
- Other surgical predictors
  - Planned admission (Pre- or post-operatively) vs. ambulatory procedure
- Patient characteristics:
  - Age (continuous);
  - Sex (binary);
- Anesthesia-related:
  - Local anesthetic type (Long-acting only vs. mixed);
  - Dexamethasone use (Present or absent);
  - Intraoperative Anesthesia (General anesthesia as defined by need for advanced airway/Sedation/Spinal).

### **Additional cohort characteristics to be reported:**

- Pre-PNB neuropathy (Present or absent; Defined as “Yes” for either Pre-PNB neuropathy or diabetic neuropathy)
- Tourniquet location (Leg versus thigh)
- Tourniquet duration
- Block performer (Attending/ Fellow/ Resident)
- Duration of sensory blockade (as defined by time from PNB performance to return of normal sensation) (Continuous variable);
- Duration of motor blockade (As defined by time from PNB performance to return of normal movement) (Continuous variable);

- Time of day the nerve block wore off (Between 0000- 0700 / Between 0701-2359) (25,26)
- Health care practitioner contact, as defined by answering “yes” to the question of “Did you have to visit the emergency department, or call the surgeon or your family doctor for pain control after your nerve block wore off?”.
- Highest pain score (HPS), as defined by the highest NRS pain score upon resolution of peripheral nerve blockade within 48 hours of block performance.

## Methods

### Data Preprocessing:

#### Categorization of Lower Limb Surgeries

In the database, the operations performed are entered as free texts, transposed from dictated operative reports. We created a standardized list of keywords and logic protocol to categorize the text variables into groups. Keywords (e.g., “total ankle replacement”) will be used to electronically identify main surgical types (e.g., Group 2 = Total Ankle Replacement). Please see Supplementary Material for a full list of keywords and their corresponding surgical types. For patients who fit into multiple surgical types based on keywords, patients will be electronically assigned to the first group on the list. For example, if a patient received both bunionectomy and hardware removal, the patient will be assigned into Group 4= Hallux Valgus Surgery. All surgical assignments will subsequently be manually checked independently by two authors ([name] and [name]), and conflicts will be resolved with a third author ([name]). To complement this manual check, Cohen’s Kappa will be computed to identify the level of agreement of the classifications between the two authors ([name] and [name]), after their respective corrections to the main surgery type classifications.

#### Missing values

Any variables with >10% missing data among observations will be excluded from the modelling stage. Any variables with <10% missing data among observations will have their missing values imputed using multiple imputation.

Since the primary variable of interest “Main surgery type” has numerous categorical levels, we intend to omit any observations that are missing a “Main surgery type” value, given the greater risk of non-convergence when attempting to impute this variable. Also, any observations with missing values in the primary outcome (rebound pain scores) will be excluded too. The remaining variables are assumed to be missing at random (MAR).

The planned method of multiple imputation will be by using multivariate imputation by chained equations (MICE). The following imputation techniques will be used to impute each variable with missing data:

- “Predictive mean matching” will be used to impute the continuous variables

- Logistic regression will be used to impute the binary variables
- Multinomial logistic regression will be used to impute the nominal categorical variables

All variables (including the outcome) will contribute to imputation of the missing values. The plan of the imputation will be to generate 10 multiply imputed datasets (with an anticipated maximum of 20 iterations to achieve convergence), which will then be used to model and pool results.

### **Cohort characteristics**

Summary statistics of outcomes and candidate predictors will be presented. Continuous variables will be presented as mean (SD) if normally distributed and median (IQR) if not normally distributed, and categorical variables will be presented as frequency (%).

### **Model building**

Correlations amongst candidate predictors will be explored to avoid risks of collinearity (for example, between dexamethasone use and type of intraoperative anesthesia). Amongst multiple highly correlated predictors, only one will be selected for the modeling based on clinical reasoning (e.g. one variable is more easily collected, less missing values, etc.). Additionally, potential multicollinearity within the final model will be diagnosed using variance inflation factors (VIF) of the predictors, with any values exceeding 4 warranting further investigation.

Multivariable logistic regression will be the statistical method used to construct a prediction model, with the above outlined imputation procedure applied to the data prior to modelling. The prediction model will contain the complete variable set as predictors (as outlined in the Candidate Predictors section). “Age”, the only continuous predictor to be included in the model, will be modelled with a natural cubic spline (with 3 interior knots).

In addition, an exploratory prediction model will be created where a natural cubic spline (with 3 interior knots) will also be fitted for an additional predictor of “Tourniquet duration”. This serves as an exploration of whether tourniquet duration plays a predictive role. However, this exploratory model could only be used postoperatively, when this information becomes available. Future database with information on predicted tourniquet duration would be needed for model update to minimize bias if this predictor were to be applied preoperatively. The primary and exploratory models will then be compared in terms of predictive performance and a likelihood ratio test will also be conducted to assess differences in goodness-of-fit.

To assess the performance of the predictive models, we will proceed with a bootstrap validation approach with 100 repetitions. At each repetition, the data will be sampled with replacement to form a bootstrap sample (with sample size equivalent to the original dataset). Multiple imputation will then be conducted on the bootstrap sample prior to modelling (using the same procedure outlined in the above “Missing values” section). After the pooled bootstrap model is created for the given bootstrap sample, performance measures (as discussed below) will be pooled across the 10 multiply imputed datasets of (1) the bootstrap sample and (2) the original

dataset. These will individually form estimates of the “training” and “test” performance, permitting us to compute the optimism of the pooled bootstrap model.

This process will be repeated for each of the repetitions, and optimism estimates will be averaged over the 100 repetitions. Lastly, an estimate of the original model performance will be computed by taking the apparent performance of the original model and subtracting the average optimism.

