## Study Description

Rebound pain is a well-recognized phenomenon after the resolution of peripheral nerve blocks. (1–5) Severe rebound pain is prevalent after ambulatory surgery, with potential resultant increased health-care utilization and cost. (6) Risk factors for severe rebound pain may include younger age, female sex, high preoperative pain score, bone surgeries, and upper limb surgeries. (7–10) Use of tourniquet for lower limb procedures is also associated with worse postoperative pain compared to without. (11,12) Protective factors may include continuous perineural catheter, regional anesthesia adjuncts, and multimodal oral pain management prior to resolution of peripheral nerve blockade. (8,9,13–17) However, placement of continuous peripheral nerve block catheters utilizes additional health care resources; hence, a targeted approach where continuous perineural catheters are offered to patients at the highest risk of severe rebound pain could potentially offer the biggest benefit. The aim of the study is to derive and validate a multivariable prediction model for severe rebound pain after lower limb surgery involving popliteal blockade, to assist with risk stratification and shared decision making.

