### Model performance measures

To assess model performance, we will use the area under the Receiver Operating Characteristic (ROC) curve (i.e., AUC) and calibration slope to evaluate the discrimination and calibration of the models, respectively. Other overall performance measures that will be computed include the Scaled Brier score and Nagelkerke’s  $R^2$ . Decile calibration plots will also be generated for the final prediction models to further assess calibration, with Loess-smoothed calibration curves created for each imputed dataset. Additionally, a decision curve analysis will be performed on the final prediction models.

Based on the final validated logistic regression models, a points system will be developed to approximate the contribution of the risk factors in the estimate of risk of having a severe rebound to increase clinical utility of the models. (27)

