### Sample size

Calculations based on estimated sample size of 1270, and event rate of 50% are shown below. (8) [<https://www.bmj.com/content/368/bmj.m441>] (Excel spreadsheet of table below available)

Binary outcomes		
Figure 1	Margin of error $\leq 0.05$	
Criteria iii in pms	Outcome proportion ->	0.5
	Total n needed	384.16
Figure 2	Mean absolute prediction error (MAPE) at 0.05 in predicted probabilities when applied to other targeted individuals	
	number of candidate variables ->	18
	Total n needed	1013.2
Figure 3	Target shrinkage of $\leq 10\%$ (i.e. shrinkage factor = .9), Rsquared CS (proportion of variation explained) at least .1	
Criteria i in pms	Total n needed	716.234
	See Fig 4 for notes: Rsq often .1-.2 for binary for medical; use .5 for direct/explanatory	
Figure 5	n participants required to ensure expected optimism of $\leq 0.05$ in the apparent Rsq	
Criteria ii in pms	Anticipated Rsq	0.2
	Ln L null	-693.15
	Max Rsq (depends on proportion)	0.75

	n Outcome	500
	n total sample size (arbitrary)	1000
	Shrinkage factor corresponding to optimism of $\leq 0.05$ in $R^2$	0.84211
	Total n needed	420.427

Estimate the overall outcome proportion with sufficient precision ( $\leq 0.05$ )	384.16
Target a small mean absolute prediction error (0.05)	1013.2
Target a shrinkage factor of 0.9	716.234
Target small optimism of 0.05 in the apparent $R^2$ Nagelkerke	420.427

Data will be analyzed using R (version 4.0.3). Any statistical tests will be two-sided, with significance levels of 0.05.

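### As written, the published equation and points-to-risk table use unshrunk coefficients, so high and low printed risks are on average about 1 to 3 points too extreme if R² is 0.1 to 0.2

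*Combined protocol and SAP*

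**What the plan says.** Under Model building, the plan states that "Multivariable logistic regression will be the statistical method used to construct a prediction model", with the full predictor set and a spline for age. A second model adds tourniquet duration: "an exploratory prediction model will be created where a natural cubic spline (with 3 interior knots) will also be fitted". Internal validation uses 100 bootstrap samples with multiple imputation in each, after which "an estimate of the original model performance will be computed by taking the apparent performance of the original model and subtracting the average optimism".

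Under Model performance measures, the calibration slope is one of the measures, so an optimism-corrected slope will be available. The same section goes on: "Based on the final validated logistic regression models, a points system will be developed". It also says "Decile calibration plots will also be generated for the final prediction models to further assess calibration" and "a decision curve analysis will be performed on the final prediction models".

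Shrinkage is named only under Sample size, as a sizing criterion: "Target a shrinkage factor of 0.9". Nothing in the plan says whether the corrected slope, or any penalty, is applied to the coefficients, the intercept or the points-to-risk table.

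**The concern.** An unpenalised logistic model has an apparent calibration slope of 1 on the data that produced it. In new patients its slope is expected to be below 1, so its predictions are too spread out. The planned bootstrap estimates by how much, but the plan uses that estimate only to describe the model. The equation and the table that clinicians would use keep the unshrunk coefficients.

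The printed absolute risk is the study's product. The stated purpose is "to assist with risk stratification and shared decision making", and the Study Description wants catheters directed to the patients most at risk. The top of the scale is where overfitting overstates risk on average. Leaving the choice open also allows it to be made after the results are known.

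**Working it through.** **Inputs.**
- Sample size: n = 1270, event rate 50%, shrinkage target 0.9.
- Cox-Snell R²: a floor of 0.1, a usual range of 0.1 to 0.2, and 0.2 in the optimism criterion.
- Parameters, from the predictor list and Model building: surgery type 8 + admission 1 + age spline 4 + sex 1 + local anesthetic 1 + dexamethasone 1 + anesthesia 2 = 18, which agrees with the plan's count. A tourniquet spline adds 4, giving 22.

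**Step 1: reproduce the plan's figure.** The formula is n = P / [(S − 1) ln(1 − R²/S)].
- With P = 18, S = 0.9, R² = 0.2: ln(1 − 0.2/0.9) = −0.25131, so n = 18 / (0.1 × 0.25131) = 716.23. This is the printed 716.234.
- With R² = 0.1: ln(1 − 0.1/0.9) = −0.11778, so n = 18 / (0.1 × 0.11778) = 1528.2. This exceeds 1270.

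The plan's label for this criterion names 0.1 as the floor, but its arithmetic uses 0.2.

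**Step 2: expected slope at n = 1270**, solving the same formula for S.

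| R² | S, 18 parameters | S, 22 parameters |
|---|---|---|
| 0.10 | 0.882 | 0.860 |
| 0.15 | 0.920 | 0.905 |
| 0.20 | 0.941 | 0.929 |

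The 0.9 target is met from R² = 0.119 upwards with 18 parameters and from 0.143 with 22.

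**Step 3: effect on printed risks.** About a 50% mean, a printed risk p corresponds on average to expit(S × logit p). For the primary model:
- R² = 0.2: logit 0.8 = 1.386, × 0.9407 = 1.304, giving 78.7% (1.35 points too high). Logit 0.9 = 2.197, × 0.9407 = 2.067, giving 88.8% (1.24 points too high).
- R² = 0.1: 1.386 × 0.8822 = 1.223, giving 77.3% (2.74 points too high). 2.197 × 0.8822 = 1.938, giving 87.4% (2.58 points too high).

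Printed risks of 20% and 10% are too low by the same amounts. The largest error is 1.4 points at R² = 0.2 and 2.8 at R² = 0.1, near a printed 83% to 84%.

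**Step 4: simulation.** This is illustrative only. It used n = 1270, 50% events, 18 parameters, assumed prevalences and effects, and no missing data. Figures are for R² = 0.1 / 0.2, from 200 simulated cohorts at each R².
- Slope in new patients: 0.87 / 0.92 unshrunk, 0.99 / 1.00 after multiplying by the bootstrap-corrected slope.
- Top decile overstated by 2.7 / 1.6 points, falling to 0.1 / 0.0 after shrinkage. Repeat runs gave 2.6 to 3.0 / 1.4 to 1.7 before shrinkage.
- Bottom decile understated by 3.2 / 1.8 points, falling to 0.6 / 0.3.
- Mean absolute prediction error: 0.0464 to 0.0444 / 0.0439 to 0.0430.
- Net benefit in new patients at illustrative thresholds of 0.3, 0.5 and 0.7 changed by −0.0001 to +0.0009.

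**The case against.** The case for leaving the plan alone is a fair one. It fixes the predictor set without outcome-driven selection, sizes the study for a shrinkage factor of 0.9, and will report an optimism-corrected slope. Controlling overfitting through sample size and reporting what remains is coherent. The simulated mean absolute prediction error is already below the plan's 0.05, net benefit barely moves, and the same patients stay at the top of the ranking. All of this stands, and it limits the point to a minor one.

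Three further objections stand in part.
- **The most extreme risks are rare when R² is low.** With a normally distributed linear predictor (an assumption), at R² = 0.1 about 3.2% of patients would have a prediction of 80% or more and about 0.17% one of 90% or more, some 2 of 1270. The 90% example at R² = 0.1 therefore concerns almost nobody. Averaged over all patients, the shift is about 1.4 points at R² = 0.1 and 0.9 at R² = 0.2. The top-decile figures do not depend on such rare patients.
- **The points table is approximate.** In an illustrative run with assumed effects and point units, rounding to integer points alone moved individual risks by about 1.7 to 3.2 points on average. Rounding error is not systematic in the way overfitting is, so it does not excuse leaving the average bias in.
- **The correction is for an average.** The shrinkage factor hardly varied between simulated cohorts (SD 0.016 and 0.008 at R² = 0.1 and 0.2), while the true slope ranged over 0.76 to 1.01 and 0.83 to 1.04 (5th to 95th percentile). Error rose slightly in roughly a quarter to 40% of cohorts.

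A reader might infer that the plan rejects shrinkage, or that the published model would misdirect treatment. The documents support neither. The plan is silent on shrinkage, not opposed to it. It gives no decision threshold, so no changed decision can be shown. Conversely, a reader might take the word validated to mean that the coefficients are corrected. The validation described corrects performance measures only.

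**Conclusion.** The point holds as a minor one. Followed as written, the plan measures the overfitting of its final model and then publishes the model without using that measurement. The resulting bias is systematic on average but small: about 1.2 to 1.4 points at printed risks of 80% to 90% if R² is 0.2, and about 2.6 to 2.7 points if it is 0.1, mirrored at the low end. Under the plan's own tolerance it is acceptable in the primary model from R² of about 0.12 upwards and missed at the floor of 0.1. The exploratory model, with 22 parameters, is slightly worse off.

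These figures rest on n = 1270, 18 parameters, a 50% event rate and R² of 0.1 to 0.2. The documents do not make clear whether 1270 is counted before or after exclusions. A smaller analysed cohort would enlarge the error: up to 3.5 points at R² = 0.1 if n were 1013, taken here only as an illustration.

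**What to change.** Add a short paragraph to the SAP, for the primary and exploratory models:

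1. After the bootstrap, multiply the pooled coefficients by the optimism-corrected calibration slope.
2. Re-estimate the intercept so that mean predicted risk equals the observed rate.
3. Take the published equation and the points-to-risk table from this shrunken model. Relative points do not change, because every coefficient is multiplied by the same factor; only the risk attached to each total changes.
4. Label the bootstrap performance measures as those of the unshrunk model.
5. Note that calibration plots of the shrunken model on the development data will show a slope above 1. The expected value is 1/S, from 1/0.941 = 1.06 to 1/0.882 = 1.13, and it is not a fault.

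The cost is that paragraph and a few lines of code, with no new data. Repeating the shrinkage inside every bootstrap sample, so that the reported measures describe the shrunken model, is optional. With an inner bootstrap it would add about 100 × 100 × 10 = 100,000 fits per model to the planned 100 × 10 = 1,000. The downside is the one conceded above: the correction is right on average but can slightly raise error in a given cohort. It has also not been tried here with imputation inside the bootstrap. If the team prefers not to shrink, the SAP should say so, and the corrected slope should be printed beside the points table.

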### Model performance measures

To assess model performance, we will use the area under the Receiver Operating Characteristic (ROC) curve (i.e., AUC) and calibration slope to evaluate the discrimination and calibration of the models, respectively. Other overall performance measures that will be computed include the Scaled Brier score and Nagelkerke’s  $R^2$ . Decile calibration plots will also be generated for the final prediction models to further assess calibration, with Loess-smoothed calibration curves created for each imputed dataset. Additionally, a decision curve analysis will be performed on the final prediction models.

Based on the final validated logistic regression models, a points system will be developed to approximate the contribution of the risk factors in the estimate of risk of having a severe rebound to increase clinical utility of the models. (27)

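### The decision curve and calibration plots are planned on the final models with no optimism correction named, so net benefit would probably be reported moderately too high

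*Combined protocol and SAP*

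**What the plan says.** Under Model building, the plan describes a bootstrap with 100 repetitions. In each one, "performance measures (as discussed below) will be pooled across the 10 multiply imputed datasets of (1) the bootstrap sample and (2) the original" dataset, and the difference gives the optimism. The reported result is then "computed by taking the apparent performance of the original model and subtracting the average optimism".

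Under Model performance measures, AUC and calibration slope are named for discrimination and calibration, with the scaled Brier score and Nagelkerke's R² as overall measures. Separate sentences cover the graphical outputs: "Decile calibration plots will also be generated for the final prediction models to further assess calibration, with Loess-smoothed calibration curves created for each imputed dataset", and "Additionally, a decision curve analysis will be performed on the final prediction models". Neither sentence mentions bootstrap repetitions or optimism, and no range of threshold probabilities is given for the decision curve.

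The Study Description gives the motive for the model: "a targeted approach where continuous perineural catheters are offered to patients at the highest risk of severe rebound pain".

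**The concern.** A model fitted by unpenalised maximum likelihood looks better on its own data than on new patients. The plan recognises this for its scalar measures. Read naturally, it does not carry the correction over to the two displays.

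For calibration, the slope of a logistic model evaluated on its own fitting data is 1 by construction (about 1 for a model pooled over imputations). An apparent calibration plot therefore shows little of any overfitting. The optimism-corrected slope would still report it, so this half of the point is the lesser one.

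For net benefit there is no such backstop. A corrected AUC or slope does not convert into net benefit at a given threshold. Net benefit is the planned output that weighs treating true positives against treating false positives, which is the trade-off behind targeting a resource-intensive catheter at high-risk patients. It would be biased upward with no corrected figure beside it.

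The plan also compares a primary with an exploratory model, and apparent curves tend to favour the larger one.

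**Working it through.** **Inputs from the plan.** Sample size: n = 1,270 and 50% events. Candidate predictors and Model building: surgery type 8 + admission 1 + age spline 4 + sex 1 + local anesthetic 1 + dexamethasone 1 + intraoperative anesthesia 2 = 18 parameters, matching the 18 in the Sample size table. The full model is fitted without outcome-driven selection.

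**The plan's own figures.** It gives none for net-benefit optimism, but its sample-size figures fix the planning values, and they reproduce:

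- Outcome proportion: (1.96/0.05)² × 0.25 = 384.16.
- Prediction error: exp[(−0.508 + 0.259 ln 0.5 + 0.504 ln 18 − ln 0.05)/0.544] = 1013.2.
- Shrinkage: n = P/[(S − 1) ln(1 − R²/S)] = 18/[(−0.1) × ln(1 − 0.2/0.9)] = 716.234, so R² = 0.2 was used.
- R² optimism: S = 0.2/(0.2 + 0.05 × 0.75) = 0.84211, giving 420.427.

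The table's label for the shrinkage criterion says at least 0.1, so both R² values are examined.

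**Expected overfitting.** Solving the shrinkage formula for S at n = 1,270 gives S ≈ 0.88 for R² = 0.1 and S ≈ 0.94 for R² = 0.2. Simulated slopes in new patients agree: about 0.87 and 0.92 to 0.94. The apparent slope was 1.00.

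**Net benefit.** NB(t) = TP/n − (FP/n) × t/(1 − t). At 50% events, treat-all gives 0.5 − 0.5 t/(1 − t), which is 0.286 at t = 0.3, 0.167 at 0.4 and 0 at 0.5. The default is therefore treat-all below 0.5 and treat-none from 0.5 upward.

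**Main simulation.** 150 replicates per setting, complete data, an assumed predictor mix with 18 parameters. The model was fitted on 1,270 patients and evaluated in 200,000 new ones. The plan gives no thresholds, so five are shown. Entries are the gain over the default; percentages are relative to the true gain.

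| R² | Threshold | Apparent | True | Excess | % of true | Bootstrap-corrected |
|---|---|---|---|---|---|---|
| 0.1 | 0.3 | 0.0153 | 0.0094 | 0.0059 | 63 | 0.0094 |
| 0.1 | 0.4 | 0.0515 | 0.0414 | 0.0101 | 24 | 0.0405 |
| 0.1 | 0.5 | 0.1422 | 0.1242 | 0.0180 | 14 | 0.1267 |
| 0.1 | 0.6 | 0.0739 | 0.0536 | 0.0203 | 38 | 0.0566 |
| 0.1 | 0.7 | 0.0249 | 0.0096 | 0.0153 | 159 | 0.0100 |
| 0.2 | 0.3 | 0.0392 | 0.0338 | 0.0054 | 16 | 0.0335 |
| 0.2 | 0.4 | 0.0946 | 0.0863 | 0.0083 | 10 | 0.0860 |
| 0.2 | 0.5 | 0.2011 | 0.1875 | 0.0136 | 7 | 0.1899 |
| 0.2 | 0.6 | 0.1391 | 0.1226 | 0.0165 | 13 | 0.1257 |
| 0.2 | 0.7 | 0.0818 | 0.0637 | 0.0181 | 28 | 0.0676 |

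The largest residual after correction is 0.0566 − 0.0536 = 0.003 at R² = 0.1 and 0.0676 − 0.0637 = 0.004 at R² = 0.2.

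**Sensitivity.**

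- *Choice of default at 0.5.* If the better default is picked within each sample, its expected apparent value is 2√(0.25/1270) × 0.399 = 0.0281 × 0.399 = 0.011. At R² = 0.1 the comparison becomes about 0.131 against 0.123, or 6%. With a second predictor mix (0.1368 against 0.1227) it falls to about 3%.
- *Predictor mix.* The second mix gave 0.006 to 0.016 (R² = 0.1) and 0.004 to 0.015 (R² = 0.2). A separately programmed simulation gave 0.007 to 0.018 and 0.006 to 0.014, with at most 0.003 left after a 100-repetition bootstrap.
- *Smaller n.* At n = 900 and R² = 0.1, the excess at threshold 0.5 was 0.022.
- *Model comparison.* Tourniquet duration adds 4 parameters (22 in all). When it was simulated as pure noise, apparent net benefit favoured the larger model at all five thresholds, by up to 0.002. In new patients the larger model was worse at all five, by 0.001 to 0.002.

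**The case against.** The strongest reply is textual. The bootstrap covers performance measures discussed below, without restricting them to scalars, and the section that follows carries that title and contains both the plots and the decision curve. Nothing says the curves are uncorrected. That stands as far as it goes: this is underspecification, not contradiction, and the size given here applies only under the apparent reading. But the Loess curves are specified per imputed dataset, with no mention of bootstrap samples, and the decision curve is tied to the final models. An analyst following the text would most likely produce apparent curves.

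Second, the consequence is limited. The corrected slope already discloses overfitting, and the decision curve is an added analysis on which no decision in the plan depends. In the main runs the true gain is positive at every threshold for both R² values. In another simulation at R² = 0.2, the optimism (0.006 to 0.014) was below the sampling standard error of the gain (0.008 to 0.019) at each threshold. At R² = 0.1, an apparent gain with no true gain arose in 0.5% of replicates, and only at threshold 0.7. All this is fair and rules out calling the problem serious. It does not remove it: sampling error is not directional, while this bias is upward on average and can be removed.

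Third, the largest percentages come from small denominators at thresholds the plan does not name. That also stands, so the absolute figures are the better guide.

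**Conclusion.** The concern holds. No optimism correction is named for the decision curve or the calibration plots, and the natural reading makes both apparent. Under that reading, net benefit is overstated by roughly 0.005 to 0.020 over thresholds 0.3 to 0.7. That is moderate in absolute terms and proportionally large only where the gain is small. It would seldom change whether the model looks useful at all, but it can flatter the size of the benefit and slightly favour the larger of the two models.

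The figures rest on an assumed predictor mix, R² between 0.1 and 0.2, assumed thresholds, 50% events, n = 1,270 and complete data. The imputation step was not simulated. A smaller analysed sample would increase the excess.

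**What to change.** State under Model performance measures that the decision curve and the smoothed calibration curve are optimism-corrected. Within each of the 100 planned repetitions, compute net benefit over the prespecified threshold grid to be reported, and the smoothed calibration curve on a fixed grid of predicted risk, in the bootstrap sample and in the original data. Subtract the average optimism. Present the corrected curves as the main displays and show the apparent curves, labelled as such, alongside. Do this for both the primary and the exploratory model.

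The cost is one sentence or two in the SAP, a few more lines in a loop that already exists, and slightly less favourable curves.

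Using the corrected slope as a uniform shrinkage factor before deriving the points system is an optional extra. It mainly affects predicted risks (in the simulation it changed net benefit by at most 0.002) and does not correct an error in the plan.
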